2.4.3 Prior, concomitant and post therapies

Concomitant medications and significant non-drug therapies prior to and after the start of the study treatment, including rescue medication therapy, will be listed and summarized according to the Anatomical Therapeutic Chemical (ATC) classification system. Surgical and medical procedures prior to and after the start of the study treatment will be listed and summarized by system organ class and preferred term.

2.4.4 Protocol deviations

The number (%) of patients with protocol deviations will be summarized by deviation category (as specified in the latest version of the study data handling plan (DHP) at the time of analysis) and overall for the FAS. All protocol deviations will be listed, flagging those leading to the exclusion of a patient from an analysis set. Protocol deviations will be listed for screening failures (if any).

2.5 Analysis of the primary objective

The primary objective is to assess ability of eltrombopag to induce sustained response off treatment by month 12 in ITP patients who relapsed or failed to respond first-line steroid treatment.

For the primary and supportive analyses the FAS will be used.

2.5.1 Primary endpoint

The primary endpoint is the proportion of patients with sustained response off treatment by month 12.

Sustained response off treatment is defined as:

- reach platelet count $\geq 100 \times 10^9 / L$ (CR) and then maintain platelet counts around $100 \times 10^9 / L$ for 2 months (no counts below $70 \times 10^9 / L$) **AND** then
- taper off the drug until treatment discontinuation (see Section 9.1 of the study protocol) while maintain platelet count $\geq 30 \times 10^9 / L$ in the absence of bleeding (no bleeding AEs) or use of any rescue therapy (see Section 6.2.3 of the study protocol),
- and maintain platelet count $\geq 30 \times 10^9 / L$ in the absence of bleeding (no bleeding AEs) or use of any rescue therapy (see Section 6.2.3 of the study protocol) until month 12.

In the first 12 months, the platelet count values from scheduled visits will be used, in the follow-up phase values from all visits (scheduled and unscheduled) will be used for the analysis of the platelet counts. See mapping of visits in Section 2.1.1 (Time windows).

2.5.2 Statistical hypothesis, model, and method of analysis

The number (%) of patients with sustained response off treatment by month 12 will be summarized together with 95% confidence interval (CI) using the Clopper-Pearson method.

A binomial test for one proportion, $H_0: P=0.15$ vs. $H_1: P>0.15$ will be performed to test if the proportion of sustained response off treatment patients is greater than 15% using a target alpha level of 0.05.

Listing for hematologic response, with flags for: platelets $<30 \times 10^9 / L$, bleeding events, transfusions, and rescue medications will be provided. Steps until sustained response off treatment at month 12 and during the follow-up period will be flagged as follows:

- Patients who reached platelet count $\geq 100 \times 10^9 / L$ at least once
- Patients who maintained stable platelet count for 2 months after reaching $100 \times 10^9 / L$ (no counts below $70 \times 10^9 / L$)
- Patients who were able to be tapered off the drug till treatment discontinuation, while maintain platelet count $\geq 30 \times 10^9 / L$ in the absence of bleeding (no bleeding AEs) or use of any rescue therapy
- Patients with sustained response off treatment until month 12, while maintain platelet count $\geq 30 \times 10^9 / L$ in the absence of bleeding (no bleeding AEs) or use of any rescue therapy
- Patients with sustained response off treatment from month 12 to month 24, while maintain platelet count $\geq 30 \times 10^9 / L$ in the absence of bleeding (no bleeding AEs) or use of any rescue therapy

The patients can re-attempt Steps 1 to 3.

The patient cannot be considered as having achieved SRoT (step 4) in the cases below:

1. If a patient has taken rescue med prior to day 14 and if the dosage was increased after day 14 they are not considered as Step 4 at month 12.
2. If a patient has taken new rescue med after day 14 they are not considered as Step 4 at month 12.
3. If a patient taken platelet transfusion after day 14 they are not considered as Step 4 at month 12.

2.5.3 Handling of missing values/censoring/discontinuations

No imputation will be used for missing platelet values.

After achieving CR, at least two platelet counts should be available (at least 14 days apart) to assess maintenance around $100 \times 10^9 / L$ for two months and to assess sustained response off treatment after tapering (if tapering ends prior to month 11).

A patient who discontinues early from the study (before month 12, e.g. withdrawal of consent) will not be considered for sustained response off treatment.

See mapping of visits in Section 2.1.1 (Time windows).

2.5.4 Supportive analyses

The number (%) of patients:

- with CR (reaching platelet count $\geq 100 \times 10^9 / L$)
- who maintained platelet counts around $100 \times 10^9 / L$ for 2 months (no counts $< 70 \times 10^9 / L$)
- who managed to start tapering eltrombopag after maintaining platelet counts around $100 \times 10^9 / L$ (no counts $< 70 \times 10^9 / L$) for 2 months
- who are able to discontinue eltrombopag after tapering

will be provided together with 95% CI using the Clopper-Pearson method.

In addition bar plot(s) for the percentage of patients in each category will be provided.

2.6 Analysis of the key secondary objective

There is no key secondary objective.

2.7 Analysis of secondary efficacy objective(s)

For all efficacy and PRO analyses, the FAS will be used. For all safety analyses the safety set will be used.

2.7.1 Secondary endpoints

2.7.2 Efficacy endpoint(s)

1. To assess the **duration of sustained response off treatment** after treatment discontinuation
 - 1a) Summary statistics for the duration of sustained response off treatment (weeks) counted from last dose of eltrombopag to month 12 for patients with sustained response off treatment

(SRoT_M12 patients) will be provided. Mean, SD, median, maximum, minimum, 25th percentile and 75th percentile will be provided.

1b) Kaplan-Maier analysis and corresponding plot for the duration of sustained response off treatment for all patients meeting the primary endpoint (SRoT_M12 patients) (weeks) will be provided and is counted from last dose of eltrombopag to relapse. The SRoT_M12 patients who do not relapse/ restart eltrombopag treatment until month 24 will be censored.

- Event: relapse after achieving SRoT_M12 (platelets <30 Gi/L, bleeding event, rescue therapy/platelet transfusion, or restarted eltrombopag treatment)
- Censoring rules: Patients with SRoT_M12 who enter follow-up and do not relapse by cut-off date/Month 24 will be censored at the earliest of discontinuation date/death date/M24 platelet assessment date/cutoff date. SRoT_M12 patients who did not enter or do not yet have platelet assessments in follow-up phase are censored at their M12 platelet assessment date.

1c) Kaplan-Maier analysis and corresponding plot for the duration of sustained response off treatment for all patients who achieved Step 3 (S3 patients) (weeks) will be provided and is counted from their last dose of eltrombopag on or before this last S3 to relapse.

The S3 patients who do not relapse/ restart eltrombopag treatment until month 24 will be censored.

The event and censoring rules are as in 1b) above.

It is noted that the SRoT_M12 patients are a subset of patients in the group of patients who achieved Step 3 (S3 patients).

Duration of SRoT (weeks) for the tapered patients who achieved step 3 will be summarized by SRoT_M12 status.

2. To assess the proportion of patients maintaining a sustained response off treatment after treatment discontinuation until month 24. Number (%) of patients who are in sustained response off treatment at months 15, 18, 21, and 24 will be provided.
3. To assess the ability of eltrombopag to induce **early response by month 1**

Number (%) of patients who reach platelet count $\geq 50 \times 10^9 / \text{L}$ at least once within the first month (month 1) without bleeding events and no rescue therapy will be provided.

4. To assess the ability of eltrombopag to induce a **recovery response**, in case of loss of response after tapering of eltrombopag

Number (%) of patients with at least one platelet count $\geq 30 \times 10^9 / \text{L}$ after eltrombopag is re-introduced, in case of loss of response ($< 30 \times 10^9 / \text{L}$ and/or bleeding event) without bleeding events and no rescue therapy will be provided.

5. To quantify the **platelet count** from baseline to 3, 6, 9, 12, 15, 18, 21, 24 months

Absolute and relative change in platelet count from baseline to 3, 6, 9, 12, 15, 18, 21, 24 months and EOT will be provided for all scheduled visits. Box plots for absolute and/or relative change in platelet counts from baseline to different time points will also be provided. Additionally, platelet counts ranges ($\geq 30 \times 10^9 / \text{L}$, $\geq 50 \times 10^9 / \text{L}$, $\geq 70 \times 10^9 / \text{L}$ and $\geq 100 \times 10^9 / \text{L}$) will be provided only for patients who reach sustained response off treatment at month 12.

6. To assess the ability of eltrombopag to maintain platelet count $\geq 30 \times 10^9/L$ within 12 months and every 3 months until month 24

Number (%) of patients who maintain a platelet count $\geq 30 \times 10^9/L$ from the first time of reaching that level to month 3, 6, 9, 12, 15, 18, 21, 24 and EOT, without bleeding events and no rescue therapy will be provided.

7. To evaluate patient reported outcomes using measures for Health-Related Quality of Life with the FACIT-Fatigue, **FACT-Th6** and **SF-36v2** questionnaires.

Change in each domain score and total score of PRO parameters: FACIT-Fatigue, FACT-Th6 and SF-36v2 questionnaires from baseline to 3, 6, 9, 12, 15, 18, 21, 24 months and EOT will be provided by SRoT_M12 status. In addition, summary statistics for the two main summary scores, the PCS and the MCS for SF36 v2 as per sustained response off treatment status (sustained response off treatment versus no sustained response off treatment) will also be provided. Listings will be provided.

Scoring for SF-36v2 will be provided by an external vendor.

8. To explore the overall impact of side effects of treatment via the **GP5** at baseline, 12 months and EOT.

Overall change from baseline score will be summarized descriptively. A listing will be provided.

9. To explore treatment satisfaction with **TSQM-9**

Overall change from baseline, 12 months and EOT score will be summarized descriptively. A listing will be provided.

10. To evaluate the safety and tolerability of eltrombopag see [Section 2.8](#).

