6.1.3 Treatment duration

Patients may participate in the study for up to 24 months depending on their response. Patients not in sustained remission at month 12 will only be treated with eltrombopag in the study for 12 months.

Patients in sustained remission at month 12 will enter the follow-up period for an additional 12 months. Patients who relapse during the follow-up period (between months 12 and 24) will be offered retreatment with eltrombopag until the end of month 24. Some of the patients might not need retreatment with eltrombopag during the follow-up period.

Patients who receive treatment options other than eltrombopag within the follow-up period will discontinue the study at that time (see [Section 9.3](#)).

Patients may be discontinued from treatment earlier due to unacceptable toxicity at the discretion of the investigator or the patient. These patients will continue to be followed as per study design but will not be considered in having achieved sustained remission for the primary endpoint.

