9.3 Additional 12 months follow-up period for responders

Patients who still have sustained remission at month 12 will be followed quarterly (every 3 months) until month 24 in order to obtain further data on response and remission duration.

Patients will be followed quarterly (every 3 months) for physical exams, adverse events, concomitant medications, hematology and chemistry laboratory assessments, and patient reported outcomes (see [Table 8-1](#) Follow-up period for responders).

In case of relapse during the follow-up period, patients will be offered a new course of eltrombopag treatment within this timeframe, starting at a dose of 50 mg (starting dose for Asian patients will be 25 mg QD, reduced as per [Section 6.1](#)).

Only patients receiving retreatment with eltrombopag will be followed until month 24. Patients re-treated with eltrombopag will be followed-up for safety for an additional 30 days (safety follow-up) after month 24. The following data should be collected during the safety follow-up: adverse events and concomitant medications. This data can be collected via telephone/email contact or at a clinic visit (as needed).

Patients who are treated with treatment options other than eltrombopag during the follow-up period will discontinue the study at that time.

Patients who discontinue prior to month 24 and not at a defined study visit (see [Table 8-1](#) Follow-up period for responders) should complete their end of follow-up / Month 24 visit.

10 Definition of adverse events and reporting requirements

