Patients with confirmed diagnosis of ITP, who have failed to respond or who have relapsed following initial response after a first-line of steroid therapy with or without intravenous immunoglobulin (IVIG) (if used as a rescue therapy) will be screened, and if eligible, will receive eltrombopag. First line of steroid therapy will be defined as: prednisone/prednisolone 0.5 to 1mg/kg/day for a minimum of 2 weeks, or minimum of 1 course of high-dose dexamethasone 20 to 40 mg/day for consecutive 4 days \pm IVIG (used as rescue therapy). Maximum exposure to high-dose steroids treatment (steroids tapering time excluded) should be limited to: 4 weeks of high dose prednisone/prednisolone or 3 courses of high-dose dexamethasone. Overall exposure to steroids must not be longer than 3 months, including period of dose tapering.

Treatment in all patients will be initiated at a dose of 50 mg eltrombopag every day (QD), allowing dose escalation up to 75 mg eltrombopag QD, as per Section 6.1.1 of the study protocol.

Dosing guidelines for patients of Asian ethnicity are provided in Section 6.1 of the study protocol.

Dosing guidelines for Japanese patients in Japan are provided in Section 6.1 of the country study protocol.

Taper-off and treatment discontinuation: Patients who reach CR (platelet count $\geq 100 \times 10^9/L$) and maintain counts around $100 \times 10^9/L$ for 2 months (no platelet count below $70 \times 10^9/L$) will be eligible for taper-off and treatment discontinuation. Duration of tapering will vary depending on the starting dose and the response of the patient: decreases in eltrombopag dose will be performed by a 25 mg reduction every 2 weeks up to 25 mg on alternate days for 2 weeks until treatment discontinuation.

Patients who successfully taper off, i.e. discontinue eltrombopag and maintain platelet count $\geq 30 \times 10^9/L$ in the absence of bleeding or use of any rescue therapy will be followed up through the duration of the trial (to month 24). In case of relapse, patients will be offered a new course

of eltrombopag treatment within this timeframe, starting at a dose of 50 mg (25 mg for S/SE Asian patients and 12.5 mg for Japanese patients in Japan).

[figure not shown]
Relapse is defined as platelet count $<30 \times 10^9/L$ and/or bleeding event and/or use of any rescue therapy.

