2.4.2 Rescue therapy

Any ITP-directed medication or therapy, other than eltrombopag, given during the trial with the aim to increase platelet count for the patients who have clinically significant bleeding will be considered a rescue therapy and must be recorded on the appropriate CRF page (Form: Concomitant Medication, the category value at the form: Rescue medication). A patient who receives rescue medication or therapy between Step 2 and Step 3 will not be eligible for Step 3. A patient who receives rescue medication or therapy between Step 3 and Step 4 will not be eligible for Step 4. A patient who receives rescue medication or therapy will not be considered in having achieved sustained response off treatment for the primary endpoint, unless the patient uses steroids ± IVIG as described below in the first 14 days of start of eltrombopag.

Steroids ± IVIG use as rescue medication:

In case of clinical need such as very low platelet count (<10×10⁹/L) and/or significant bleeding, treatment with steroids ± IVIG and platelet transfusion is permitted together with eltrombopag for the first 14 days, calculated from the first dose day of eltrombopag. Any rescue therapy started before Day 14 may be used after Day 14 if the dose is considered low dose as per protocol definition and is being tapered down (i.e., successively lower doses after day 14).

Rescue medication will be taken from the SDTM cm.sas7bdat dataset where cmcat='RESCUE MED' for rescue therapy and exported as an EXCEL file. The clinical team will review the records captured in an Excel spreadsheet. Medications which were not considered as rescue therapy were flagged as 'Y' for the column 'NOT_RESCUE'. Per protocol, medications prior to Day 14 are not considered as rescue medication in the efficacy derivations and will be programmatically excluded. Medications that started prior to Day 14 and were still being tapered after Day 14 will also be programmatically excluded from efficacy derivations.

Once the database has locked the data will be rechecked again for any changes or new data that needs flagging.

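### In the response-duration Kaplan-Meier analyses, a responder who starts a non-eltrombopag ITP therapy not classed as rescue is censored at study exit, while restarting eltrombopag is always an event

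*SAP*

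**What the plan says.** **Study exit.** Protocol 9.3: "Patients who are treated with treatment options other than eltrombopag during the follow-up period will discontinue the study at that time". Protocol 6.1.3 and the first footnote to the follow-up part of Table 8-1 say the same.

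**Event.** SAP 2.7.2, item 1b: "Event: relapse after achieving SRoT_M12 (platelets <30 Gi/L, bleeding event, rescue therapy/platelet transfusion, or restarted eltrombopag treatment".

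**Censoring.** Among month-12 responders in the follow-up period, those who "do not relapse by cut-off date/Month 24 will be censored at the earliest of discontinuation date/death date/M24 platelet assessment date/cutoff date". A responder with no platelet assessment in follow-up is censored at the month-12 assessment. For item 1c, which covers all patients who tapered off successfully (Step 3): "The event and censoring rules are as in 1b) above".

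**Rescue therapy.** On ITP-directed treatment that is not eltrombopag, SAP 2.4.2 states that whatever is "given during the trial with the aim to increase platelet count for the patients who have clinically significant bleeding will be considered a rescue therapy". In the data it is found through the category RESCUE MED in the concomitant-medication records, after which the clinical team may flag individual records as not rescue. A separate search of medication and procedure records looks only for platelet transfusions.

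**Relapse.** SAP 1.1 defines it as a count below 30 × 10⁹/L "and/or bleeding event and/or use of any rescue therapy". The same section lets patients with a perceived risk of serious bleeding receive rescue at any platelet count.

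**The concern.** Items 1b and 1c estimate how long a response lasts off treatment. The event list already accepts that resuming treatment ends such a response: restarting eltrombopag counts, with no condition on platelet count or bleeding. Starting a different ITP therapy ends an off-treatment response just as surely, but it has no entry of its own. Because the protocol removes that patient from the study, the exit date becomes a censoring date.

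Kaplan-Meier estimation assumes that a censored patient has the same later risk as those still followed. A patient censored because new ITP treatment was started does not fit that assumption. At stake is the estimate of response through month 24, which the 12-month extension was added to provide.

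**Working it through.** **1. Setting the rules side by side.** The possible courses of a month-12 responder in follow-up are:

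| Course in follow-up | Listed event? | Handling |
|---|---|---|
| Recorded count < 30 × 10⁹/L | Yes | Event |
| Bleeding event | Yes | Event |
| Therapy recorded as rescue, or platelet transfusion | Yes | Event |
| Eltrombopag restarted | Yes | Event |
| Other ITP therapy, with none of the above recorded | No | Must leave the study; censored |

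Only the last row is a gap. It can be populated because rescue is tied to clinically significant bleeding and to the RESCUE MED category. A planned second-line drug entered as an ordinary concomitant medication would not be picked up. Nor would a splenectomy entered as a procedure, since the procedure search is for platelet transfusions.

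**2. Size.** The plan states no figure for this analysis, so there is none to reproduce. The following is an illustration on assumed counts.

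Inputs:
- Enrolled patients: 105 (SAP 1).
- Planning response rate: 25% (SAP 3.1.1), so 0.25 × 105 = 26.25, taken as 26 responders.
- Assumed: 4 other relapses, one each at months 15, 18, 21 and 24.
- Assumed: k switchers who meet no listed event criterion, all switching at month 15 or all at month 21.
- Simplification: time runs in study months, whereas the SAP counts weeks from the last eltrombopag dose.

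Formula: S(24) = product over event times of (1 − d/n), where d is the number of events and n the number at risk.

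One switcher:
- Censored at month 15: 25/26 × 23/24 × 22/23 × 21/22 = 0.841.
- Censored at month 21: 25/26 × 24/25 × 23/24 × 21/22 = 0.844.
- Counted as an event: 21/26 = 0.808.

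| Switchers | Censored, month 15 | Censored, month 21 | Counted as event | Overstatement (points) |
|---|---|---|---|---|
| 1 | 0.841 | 0.844 | 0.808 | 3.4 to 3.7 |
| 2 | 0.836 | 0.842 | 0.769 | 6.7 to 7.3 |
| 4 | 0.824 | 0.838 | 0.692 | 13.2 to 14.6 |

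With 26 responders and 0 to 8 other relapses, one switcher moves the estimate by 2.8 to 3.8 points. Over 23 to 32 responders (23 is the revised cut-off in SAP 3.1.2; 32 is about 30% of 105), 0 to 8 other relapses and 1 to 4 switchers, the overstatement is 2.5 to 17.4 points. It is zero if every switcher first meets a listed criterion.

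**3. The median.** Every estimate in the table exceeds 0.5, so the median is not reached by month 24 under either rule. In the wider range, only the most extreme case (23 responders, 8 other relapses, 4 switchers) crosses one half: 0.478 with switches as events, against 0.591 to 0.625 with censoring.

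**The case against.** The strongest reply is that the event list already does most of the work. A count below 30, a bleed, rescue therapy or a platelet transfusion is an event whatever happens next, because the censoring rule applies only to patients who have not relapsed. Follow-up uses counts from unscheduled as well as scheduled visits (SAP 2.5.1), and a patient who leaves between visits should complete the end-of-follow-up visit, which includes haematology. Protocol 1.1 says treatment is seldom needed above 20 to 30 × 10⁹/L, so few switches should occur without a qualifying count.

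This stands as a limit on scope. A reader might infer that every responder who switches therapy is censored; the documents do not support that. It does not close the gap, however. Scheduled visits are quarterly, unscheduled counts help only if taken and recorded, and a count at the exit visit may come after the new therapy began.

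One could also defend censoring as a deliberate choice to estimate duration as if no switch had occurred. The SAP does not say so, and treating an eltrombopag restart as an event points the other way.

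Two further limits stand. Forced exit applies only in the follow-up period. Before month 12, use of prohibited treatment stops study drug, but under Protocol 9.1.1 the patient is not considered withdrawn unless consent is withdrawn, so the argument reaches only the follow-up part of 1c. The analyses are also secondary and carry no hypothesis test.

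**Conclusion.** The gap is real but narrow. Read literally, SAP 2.7.2 censors a follow-up responder who starts a non-eltrombopag ITP therapy with no recorded count below 30 × 10⁹/L, no bleeding event and no rescue or transfusion record, although that therapy is what ends both the off-treatment response and study participation. The censoring is informative, and the bias, relative to counting the switch as an event, is upward: about 3 to 4 percentage points at month 24 per affected patient, assuming about 26 responders. The documents do not give the number of such patients.

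Three stronger readings are not supported:
- That these patients are analysed as remaining in response to month 24. They leave the risk set at censoring; the fault is the assumption that their later risk equals that of patients still followed.
- That the median, which is the stated endpoint, is shown to be biased. In the main illustration it is not reached under either rule.
- That the primary endpoint is affected. It is settled at month 12, before this exit rule applies.

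How wide the gap is also depends on an unresolved definition. SAP 1.1 describes rescue for a perceived risk of serious bleeding, while SAP 2.4.2 ties rescue to clinically significant bleeding. Whether a patient treated for perceived risk has an event or is censored depends on which text is applied.

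**What to change.** - In SAP 2.7.2, add to the event list for 1b, and for the follow-up part of 1c: *start of any ITP-directed therapy other than eltrombopag, whether or not classed as rescue; event date = start date of that therapy*.
- Identify these patients from concomitant-medication records, procedure records and the recorded reason for study discontinuation, not from the RESCUE MED category alone.
- In item 2, count them as not in SRoT at every later time point among months 15, 18, 21 and 24.
- Reconcile the rescue wording in SAP 1.1 with that in SAP 2.4.2. This is a matter for the trial team; the analysis needs only one consistent definition.

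The cost is one phrase in the SAP and some programming on data already collected. The downside is that the estimated duration may be slightly shorter. The SAP's last update is dated before the final database lock, so the rule belongs in that version. If the list is left as it stands, a sensitivity analysis with these switches as events is the minimum.

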9.1.2 Lost to follow-up

For patients whose status is unclear because they fail to appear for study visits without stating an intention to discontinue or withdraw, the investigator must show "due diligence" by documenting in the source documents steps taken to contact the patient, e.g. dates of telephone calls, registered letters, etc. A patient should not be considered as lost to follow-up until due diligence has been completed or until the end of the study.

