12.5.1 Efficacy endpoint(s)

1. To assess the **duration of sustained remission** after treatment discontinuation

1a) Summary statistics for the duration of sustained remission (weeks) counted from last dose of eltrombopag to month 12 for patients with sustained remission (R) will be provided.

1b) Kaplan-Maier analyses for the duration of sustained remission (weeks) counted from last dose of eltrombopag to relapse for patients with sustained remission (R) at month 12 and who enter 12 months follow-up period. The patients who do not relapse/die by month 24 will be censored.

1c) Kaplan-Maier analyses for the duration of sustained remission (weeks) counted from last dose of eltrombopag to relapse for all patients. The patients who do not relapse/die by month 24 will be right-censored. The duration will be considered as 0 for patients who do not manage to taper off eltrombopag per protocol i.e. do not reach sustained remission.

2. To assess the proportion if patients maintaining a sustained remission after treatment discontinuation until month 24.

Number (%) of patients who are in sustained remission at months 15, 18, 21, and 24 will be provided.

3. To assess the ability of eltrombopag to induce **early response by month 1**

Number (%) of patients who reach platelet count $\geq 50 \times 10^9/L$ at least once within the first month (month 1) without bleeding events and no rescue therapy will be provided.

4. To assess the ability of eltrombopag to induce a **recovery response**, in case of loss of response during or after tapering of eltrombopag

Number (%) of patients with at least one platelet count $\geq 30 \times 10^9/L$ after eltrombopag is re-introduced, in case of loss of response ($< 30 \times 10^9/L$ and/or bleeding event) without bleeding events and no rescue therapy will be provided.

5. To assess the **platelet count** from baseline to 3, 6, 9, 12, 15, 18, 21, 24 months

Absolute and relative change in platelet count from baseline to 3, 6, 9, 12, 15, 18, 21, 24 months and end of treatment will be provided. Box plots for absolute and/or relative change in platelet counts from baseline to different time points will also be provided.

6. To assess the ability of eltrombopag to **maintain platelet count $\geq 30 \times 10^9/L$** within 12 months and every 3 months until month 24

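### SAP items 1b and 1c censor some leavers at the discontinuation or death date instead of the last platelet count, and censor death without declaring the change from the protocol

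*SAP*

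**What the plan says.** Protocol 12.5.1 measures duration from the last eltrombopag dose to relapse. For item 1b it adds: "The patients who do not relapse/die by month 24 will be censored". Item 1c has the same rule: "The patients who do not relapse/die by month 24 will be right-censored".

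SAP 2.7.2 rewrites this for 1b: "The SRoT_M12 patients who do not relapse/ restart eltrombopag treatment until month 24 will be censored". Its event list is a platelet count below 30, a bleeding event, "rescue therapy/platelet transfusion, or restarted eltrombopag treatment". Death is not in it. A patient with follow-up data and no relapse "will be censored at the earliest of discontinuation date/death date/M24 platelet assessment date/cutoff date". The remaining group is handled differently: "SRoT_M12 patients who did not enter or do not yet have platelet assessments in follow-up phase are censored at their M12 platelet assessment date". Item 1c takes over the event and censoring rules of 1b.

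After month 12, visits with hematology are scheduled every three months (Protocol 9.3 and Table 8-1), with a window of 7 days either side. SAP section 4 records for section 2.7.2 only that the description was updated and that an event description and censoring rules were added. Death is not mentioned there.

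**The concern.** The platelet criterion for relapse can be met only when a count is taken. Completers and patients with no follow-up count are censored on the date of a count (M24 or M12). Patients who leave between these points, after at least one follow-up count, are censored on an administrative or death date. If no count was taken on leaving, the time since the last one enters the analysis as remission. The SAP gives no reason for treating this group differently, and any resulting bias lengthens the estimated duration.

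The second issue is separate. Under the protocol wording, a patient who dies is not among those censored. Under the SAP, the death date is a censoring date. That changes what the curve describes: remission ended by relapse or death, against time to relapse with death treated as non-informative censoring. SAP section 1 says that the primary CSR was already final when this addendum was written for an open-label trial, so a change in the status of an outcome should be visible to readers.

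**Working it through.** **Plan's own figures.** The plan gives no figure for the duration analysis. The design figure for the primary test reproduces: N = 105 with cut-off 23 gives an exact binomial alpha of 0.0373 and power of 0.7995 (stated 0.037 and 0.800). It is used here only for scale: 25% of 105 is 26.25, about 26 responders.

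**Length of the gap.** A month is 30.4375 days (SAP 2.1.1).
- One visit interval: 3 × 30.4375 / 7 = 13.0 weeks.
- With both 7-day windows: (91.3 + 14) / 7 = 15.0 weeks.
- Last count at M15, date recorded at M24: 9 × 30.4375 / 7 = 39.1 weeks.
- Count taken on leaving: 0.

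**Effect on the curve (illustrative model).** Assume that relapse is exponential after month 12, is detected at the four quarterly visits, and leaves a fraction S relapse-free at month 24. A fraction p is lost at times unrelated to relapse, p/4 in each quarter. Let s = S^(1/4). At visit j:
- at risk and counted = (1 − p + (4 − j)p/4) × s^(j−1)
- at risk but not counted, worst case (date recorded as month 24) = sum over k = 2 to j of (p/4) × s^(k−1). The sum starts at k = 2 because patients lost before M15 have no follow-up count and "are censored at their M12 platelet assessment date".
- hazard = (1 − s) × counted / (counted + not counted)

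For S = 0.70 and p = 0.20, s = 0.9147:

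| Visit | Counted | Not counted | Hazard |
|---|---|---|---|
| M15 | 0.950 | 0 | 0.0853 |
| M18 | 0.823 | 0.046 | 0.0808 |
| M21 | 0.711 | 0.088 | 0.0760 |
| M24 | 0.612 | 0.126 | 0.0708 |

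Estimate: 0.9147 × 0.9192 × 0.9240 × 0.9292 = 0.722.

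If the recorded date is the next missed visit, only the k = j term remains (for j of 2 or more). Estimated percentage relapse-free at month 24:

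| Recorded date | True 70%, 20% lost | True 70%, 30% lost | True 50%, 20% lost | True 50%, 30% lost |
|---|---|---|---|---|
| Month 24 (worst case) | 72.2 | 73.4 | 53.4 | 55.2 |
| Next missed visit | 71.1 | 71.8 | 51.6 | 52.6 |
| Before next visit, or last count | 70 | 70 | 50 | 50 |

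A simulation of the same model agrees within 0.1 point (72.2, 73.3, 53.5 and 55.1 in the first row; 71.1, 71.7, 51.7 and 52.5 in the second).

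The zero bias in the last row depends on all patients sharing the same visit times. The SAP counts time from last dose, so visits do not line up across patients. A second simulation used that scale. It assumed 26 or 35 responders, 12-month relapse of 20% or 40%, dropout of 10% or 30%, death of 4%, time off drug at month 12 uniform over 4 to 36 weeks, 30% of relapses found between visits, and leavers dated at their true leaving time. At week 60, moving to last-count censoring lowered the estimate by 0.2 to 0.8 points when leavers had no final count, and by 0.1 point or less when they had one.

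**Death.** One death counted as an event multiplies the curve by 1 − 1/n, where n is the number at risk. From a curve still at 100% the drop is 1/26 = 3.8 points, 1/20 = 5.0 or 1/10 = 10.0. Under the SAP it is 0. In the second simulation, counting death as an event lowered the week-60 estimate by a further 2 to 3 points.

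**The median, which is the named endpoint.** With 20% relapse the typical run did not reach a median under any rule. With 35 responders, 40% relapse, 30% dropout and no final count, the typical estimated median was 86.8 weeks under the SAP, 85.8 with last-count censoring, and 83.2 with death also counted as an event.

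**The case against.** Several safeguards narrow the gap. Protocol section 8 asks for a visit with all final assessments as soon as possible after premature discontinuation. Section 9.3 and the follow-up table ask early leavers to complete the month 24 visit, which includes hematology. SAP 2.5.1 uses unscheduled counts in follow-up. Where these work, leaving date and last count nearly coincide. They cannot work for a patient who is lost or dies.

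Four stronger readings are tempting and are not supported.

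- A reader might infer 39 weeks as the usual credit, because Protocol 9.1.2 says: "A patient should not be considered as lost to follow-up until due diligence has been completed or until the end of the study". That governs when a patient may be called lost. It does not say which date is recorded as discontinuation, so 39 weeks is an upper bound under one recording practice.
- A reader might carry every lost patient to month 24. In the model above that gives 73.6% and 75.4% (truth 70%) and 55.7% and 58.6% (truth 50%) at 20% and 30% loss. The SAP's M12 rule removes everyone lost before M15, so these figures overstate the bias.
- A reader might call all time after the last count unobserved. Bleeding, rescue and restart of eltrombopag are also events, and Protocol 9.1.1 asks for telephone contact, preferably on the visit schedule, when patients cannot attend. What is missing is mainly the platelet criterion.
- A reader might say that the protocol states that death is an event. It does not: duration runs to relapse, and death's status is inferred from the censoring sentence. Censoring death in a time-to-relapse analysis is defensible if it is declared.

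What remains is the inconsistent choice of date and a change for death that the SAP does not name.

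**Conclusion.** The point holds in a limited form. Relapse-free leavers with at least one follow-up count are the only group that the SAP does not censor at a platelet assessment. Without a final count, each can be credited with up to about 13 weeks (15 with windows), and with more only if close-out dates are recorded late. In the quarterly model the bias is 0 when the date precedes the next visit, about 1 to 3 points at the next missed visit, and about 2 to 5 points under worst-case dating, for 20% to 30% loss. Loss that follows an unseen relapse would make it larger. The loss, relapse and death rates are assumptions; the documents give none for this analysis.

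Per case, death matters more than the leaving date: about 4 points for one death at 26 at risk, and more later on. The protocol implies one treatment and the SAP applies the other without saying so.

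This is a descriptive secondary analysis. The primary test of the month 12 response rate does not depend on it.

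**What to change.** In items 1b and 1c, censor every patient without an event at the last platelet assessment on or before discontinuation, month 24 or the cut-off, whichever is earliest. This also brings the rule into line with the one for completers and for patients with no follow-up count.

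For death, choose one of two routes:
- follow what Protocol 12.5.1 implies, counting death without prior relapse as an event, with a death-censored sensitivity analysis; or
- keep death as censoring, give the reason, and show death as an event in the sensitivity analysis.

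Either way, state in SAP section 4 how the handling of death relates to the protocol wording.

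The cost is one date variable, one event rule, a few sentences of SAP text and one extra run. No new data are needed. Estimated durations may be slightly shorter.
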